## Evobrutinib

### Phase IIb in Rheumatoid Arthritis MS200527-0060

---

19. Presence of uncontrolled or New York Heart Association (NYHA) Class 3 or 4 congestive heart failure.
  - a. NYHA Class 3: Cardiac disease resulting in marked limitation of physical activity. Subjects are comfortable at rest. Less than ordinary activity causes fatigue, palpitation, dyspnea, or anginal pain
  - b. NYHA Class 4: Cardiac disease resulting in inability to carry on any physical activity without discomfort. Symptoms of heart failure or the anginal syndrome may be present even at rest. If any physical activity is undertaken, discomfort is increased.
20. History of splenectomy at any time and/or history of infected joint prosthesis if that joint prosthesis is still in place
21. History of any major surgery or joint surgery within 2 months prior to Screening, or will require major surgery or any planned joint surgery during trial
22. History of myocardial infarction or cerebrovascular event within 6 months prior to Screening, or current active angina pectoris, symptomatic heart failure, seizures, untreated hypertension, gastrointestinal bleeding, or any other significant medical condition in the Investigator's opinion
23. On anti-coagulation or anti-platelet therapy other than low dose daily aspirin for cardioprotection
24. On fish oil (unless discontinued prior to first dose)
25. History of cancer, except adequately treated basal cell or squamous cell carcinoma of the skin (no more than 3 lesions requiring treatment in lifetime) or carcinoma in situ/cervical intraepithelial neoplasia of the uterine cervix, unless considered cured > 5 years
26. Breastfeeding/lactating or pregnant, or discontinued lactation within 3 months of randomization. Lactating women are excluded regardless of whether or not they are nursing infant(s).
27. Clinically significant abnormality on ECG, or an active infective process or any other clinically significant abnormality on Screening CXR. If a CXR has been taken within the previous 3 months prior to Screening and results are available and normal, the CXR does not need to be carried out.
28. Estimated glomerular filtration rate (eGFR) < 45 mL/min/1.73 m^2 as calculated by the 4 component Modification of Diet in Renal Disease (MDRD) equation by the central laboratory:
  - a. The 4-component Modification of Diet in Renal Disease equation ([Levey 2006](#)):  
$$\text{eGFR} = 175 \times (\text{serum creatinine in mg/dL})^{-1.154} \times (\text{age in years})^{-0.203} \times 0.742 \text{ (if female)} \times 1.212 \text{ (if race is black)}.$$
29. TSH < 0.01 or ≥ 7.1 mIU/L. Subjects receiving thyroxine as replacement therapy may participate in the study provided that thyroxine has been at a stable dose for ≥ 12 weeks, and

TSH is within the reference range. TSH may be repeated once within approximately 2 weeks of the initial testing, if the first result is exclusionary, and the value from repeat testing may be accepted for eligibility to participate in the study if it is within the reference range.

30. Alanine aminotransferase (ALT), aspartate aminotransferase (AST), amylase, or lipase  $> 2 \times$  above upper limit of normal (ULN) of laboratory reference range, total bilirubin  $> 1.5 \times$  ULN, any other clinically significant laboratory abnormality
31. B cell (CD19) count  $< 50\%$  of the lower limit of normal (LLN)
32. Significant cytopenia, including absolute neutrophil count  $< 1,500/\text{mm}^3$ , platelet count  $< 100,000/\text{mm}^3$ , or absolute lymphocyte count  $< 1,000/\text{mm}^3$
33. Has taken an investigational drug within 1 month or 5 half-lives of the investigational drug, whichever is longer, prior to Screening (exclusion criteria 6 to 8 and 10 take priority)
34. Subjects currently receiving (or unable to stop using prior to receiving the first dose of IMP) medications or herbal supplements known to be potent (strong or moderate) inhibitors of cytochrome P450 isozyme 3A (CYP3A) (must stop at least 1 week prior to dosing), potent (strong or moderate) inducers of CYP3A (must stop at least 3 weeks prior to dosing), or drugs mainly metabolized by CYP3A with a narrow therapeutic index (must stop at least 1 day prior to dosing), see [Table 9](#).
35. History of/or current alcohol, substance, or drug abuse:
  - a. Excessive alcohol use is defined as alcohol and/or substance abuse or dependence (as defined by the Diagnostic and Statistical Manual of Mental Disorders, 4th edition, Text revision) in the past year **OR**
  - b. A history of alcohol or substance abuse, as determined by the Investigator.
36. Legal incapacity or limited legal capacity.
37. Positive serum  $\beta$ -D-glucan test (Japan only).

## 5.4 Criteria for Randomization and Initiation of Trial Treatment

Randomization should occur on Day 1 after all Screening procedures have been completed; subject eligibility must be reviewed again and confirmed at the site on Day 1 prior to randomization. If a subject does not meet eligibility criteria, the subject can be retested and rescreened once at the Investigator's discretion as described in [Section 7.1.1](#).

Eligible subjects will be randomized to treatment through a central randomization process by an IWRS. This will be a double-blind trial. Subjects will be stratified by whether or not they are in the MRI substudy and by region. There are no systematic differences between MRI and non-MRI sites beyond the availability and suitability of MRI for study purposes, to avoid potential selection bias. Participation in the MRI substudy will be mandatory for subjects participating at designated MRI sites.

## 5.5 Criteria for Subject Withdrawal

Subjects will be informed they have the right to withdraw from the trial at any time, without prejudice to their medical care, and they are not obliged to state a reason for withdrawing. Any withdrawal must be fully documented in the eCRF and source documents, and should be followed up by the Investigator.

The Investigator may withdraw a subject at any time if this is considered to be in the subject's best interest.

### 5.5.1 Withdrawal from Trial Therapy

Subjects who withdraw from therapy must return for an End of Treatment/Early Withdrawal Visit followed by a Safety Follow-up Visit. At the time of early withdrawal from trial therapy, all information/assessments noted at the End of Treatment Visit in the Schedule of Assessments are to be completed. For any subject that withdraws from the MRI substudy prior to Week 12, contact the Study Sponsor. If the IMP is prematurely discontinued, the primary reason for discontinuation must be recorded in the appropriate section of the eCRF, and all efforts will be made to complete and report the observations as thoroughly as possible. A complete final evaluation at the time of the subject's withdrawal should be made and any AEs followed up until resolution or a period of 30 days after the last Safety Visit (or withdrawal from the trial).

A subject must be withdrawn from IMP if any of the following occur:

- Adverse events, if permanent discontinuation of the IMP is desired or considered necessary by the Investigator and/or subject
- Use of prohibited medications, as defined in Section 6.5.2. However, any medications may be administered to address adverse reactions, or emergency situations. Should a prohibited medication be needed during the study, the subject would be withdrawn from the trial. All medications other than study therapy given during the course of the trial must be recorded (see Section 6.5.1).
- Interruption of MTX more than twice in a period of 4 weeks
- Pregnancy (for further details in case of pregnancy, see Section 7.4.2)
- Protocol noncompliance judged as significant by the Investigator and/or the Sponsor. If a subject has failed to attend scheduled trial assessments or had failed to comply with the trial protocol otherwise, the Investigator must determine the reasons and the circumstances as completely and accurately as possible.
- Subject withdrawal of consent
- Loss to follow-up; at least 3 attempts (2 telephone calls, 1 Acknowledgement of Receipt letter) should be made to contact the subject to ensure the reason for not returning is not an AE
- Death

- Participation in another clinical trial, with the exception of noninterventional studies
- Any event(s) that endanger the safety of the subject, with the exception of AEs that will be handled as above
- If during the study, in the opinion of the Investigator, the subject's RA disease level is unacceptably high requiring therapy not permitted per the protocol, the subject may withdraw from the study treatment and initiate therapy recommended per the treating physician. In this case, the subject will be considered a nonresponder.

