## 8 Statistics

### 8.1 Sample Size

The primary endpoint of the trial is the ACR20 response at Week 12.

A sample size of 80 evaluable subjects per group will provide approximately 90% power at an  $\alpha$  of 0.05, 2-sided significance level to detect a difference in Week 12 ACR20 response proportion between evobrutinib- and placebo-treated subjects, assuming a placebo response proportion of 30% to 45% and an expected treatment benefit of 30%, after adjusting for multiple comparisons

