## **8.5.2 Analysis of Primary Endpoint**

### **8.5.2.1 Efficacy Endpoints**

The primary analysis of ACR20 at Week 12 will be based on the mITT analysis set using Last Observation Carried Forward for imputation of missing values of each ACR component. A subject will be considered as a nonresponder if the subject discontinues prior to Week 12.

The estimate of the odds ratio (OR), together with the associated 2-sided 95% CI and p-value, comparing each evobrutinib dose group to placebo, will be provided based on a logistic regression model for the odds of ACR20 response, with evobrutinib dose group or placebo as a factor and adjustment for covariates based on randomization strata (region, MRI-substudy participation). In order to further characterize the dose-response, the proportion of ACR20 response at Week 12 will also be presented for each treatment group, along with the difference in ACR20 response proportion between evobrutinib and placebo, and the 95% CI for the difference. Details will be provided in the SAP.

The dose response will also be assessed via a modeling approach as additional supportive analyses. Details will be provided in the SAP.

Additional sensitivity analyses will be performed to assess the robustness of the primary missing data imputation method and will be described in detail in the SAP.

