**Table 13 : Analysis of the Primary Endpoint – ACR20 Response Rate at Week 12**

Analysis Set	Analysis method	Description	Missing data handling

 
mITT set
 
PP set
 
	Primary analysis: logistic regression	Presentation of response rate for each treatment group, difference [ $\Delta$ ] in response rate compared to placebo, 2-sided 95% CI of $\Delta$ (non-stratified MN), OR, 2-sided 95% CI of OR, 2-sided nominal p-value, and adjusted p-value (using Hochberg procedure). Adjusted p-values reported only for primary analysis based on mITT set.	LOCF-NR*

 
mITT set
 
PP set
 
	Supportive analysis no. 1: Stratified difference of response rate	Presentation of response rate for each treatment group, $\Delta$ in response rate compared to placebo, 2-sided 95% CI of $\Delta$ and 2-sided nominal p-value.	LOCF-NR*

 
mITT set
 
	Supportive analysis no. 2: Tipping Point	Presentation of p-values and response rate for each treatment group at the tipping point.	Tipping point analysis

 
mITT set
 
	Supportive analysis no. 3: Stratified difference of response rate using multiple imputation with Missing At Random (MAR) pattern	Presentation of response rate for each treatment group, $\Delta$ in response rate compared to placebo, 2-sided 95% CI of $\Delta$ and 2-sided nominal p-value.	The ACR20 will be derived using imputed ACR Components. These components will be imputed using Multiple Imputation Procedure with MAR pattern for discontinuations due to reasons other than safety or efficacy

 
mITT set
 
	Supportive analysis no. 4: Stratified difference of response rate using multiple imputation with Missing Not At Random (MNAR) pattern	Presentation of response rate for each treatment group, $\Delta$ in response rate compared to placebo, 2-sided 95% CI of $\Delta$ and 2-sided nominal p-value.	The ACR20 will be derived using imputed ACR Components. These components will be imputed using Multiple Imputation Procedure with MNAR pattern, using control-based approach, regardless of reasons for treatment discontinuation.

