### **Primary analysis: logistic regression**

For the primary analysis, the estimate of the odds ratio (OR), together with the associated 2-sided 95% CI, nominal p-value and adjusted p-value, comparing each evobrutinib dose group to placebo, will be provided based on a logistic regression model for the odds of ACR20 response, with treatment group as a factor and adjustment based on region. An example of SAS code is available in Appendix 18.5.

Missing data will be handled using LOCF-NR as follows: each component will be imputed using post-baseline LOCF (ie, baseline value cannot be used for missing data imputation). Then the ACR20 will be re-calculated using imputed components. Subjects who prematurely discontinued from treatment will be considered as non-responders.

A family-wise Type I error rate (FWER) at the primary analysis will be controlled at the 2-sided 0.05 significance level for the 3 pairwise comparisons of evobrutinib dose versus placebo, using the Hochberg procedure (see Hochberg 1990).

The statistical test comparing each evobrutinib group to placebo can be written as follows:

$$\begin{cases} H_0: OR = 1.0 \\ H_1: OR \neq 1.0 \end{cases}$$

Consider the ordered two-sided p-values (from lowest to highest) that arise from comparing the 3 comparisons on the basis of the primary endpoint:  $p_{(1)} \leq p_{(2)} \leq p_{(3)}$ . The Hochberg's step-up method proceeds as follows:

1. Step 1: If  $p_{(3)} < 0.05$  reject  $H_{(1)}$ ,  $H_{(2)}$  and  $H_{(3)}$  (i.e., conclude all evobrutinib dose groups are more effective than placebo under the condition the OR are  $> 1$ ) and then stop; otherwise go to Step 2.
2. Step 2: If  $p_{(2)} < 0.025$  reject  $H_{(1)}$  and  $H_{(2)}$  (i.e., conclude doses associated with  $H_{(1)}$  and  $H_{(2)}$  are more effective than placebo under the condition the OR are  $> 1$ ) and then stop; otherwise go to Step 3.
3. Step 3: If  $p_{(1)} < 0.0167$  reject  $H_{(1)}$  (i.e., conclude that only one of the dose groups associated with  $H_{(1)}$  is more effective than placebo under the condition the OR is  $> 1$ ) and stop

Hochberg procedure will be computed with SAS® (see Appendix 18.5). Adjusted p-values will not be presented for any analyses based on PP analysis set.

In addition, the number and percentage of ACR20 responders (Yes/No) at Week 12 will be summarized by treatment group.

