### **Supportive analysis no. 2: Tipping Point**

Subjects with reason of treatment discontinuation related to safety or efficacy will be considered as non-responders.

Tipping point analysis will be performed as in Yan 2009, Section 2.3.2.

Let

$n_1 =$  number of responders out of missing data due to various reasons for placebo

$n_2 =$  number of responders out of missing data due to various reasons for evobrutinib 25 mg QD

$n_3 =$  number of responders out of missing data due to various reasons for evobrutinib 75 mg QD

$n_4 =$  number of responders out of missing data due to various reasons for evobrutinib 50 mg BID

The same analysis method as the primary analysis of the ACR20 at Week 12 will be performed using the mITT Analysis Set for each possible combination of  $n_1$ ,  $n_2$ ,  $n_3$  and  $n_4$ .

Using the Hochberg procedure, the values of  $n_1$ ,  $n_2$ ,  $n_3$  and  $n_4$  where the study result will be tipped from statistically significant (not statistically significant) to not statistically significant (statistically significant) will be assessed for plausibility based on the corresponding response rate from each treatment.

---

**Supportive analysis no. 3: Stratified difference of response rates with imputed ACR components using multiple imputations (MAR pattern)**

The same method for estimating stratified difference of response rates will be applied, but the ACR components will be imputed using multiple imputations process (MI SAS procedure) with MAR pattern, as if they follow their original assignment of treatment group.

Data will be imputed for subjects with reason of discontinuation unrelated to safety or efficacy. Subjects with reason of treatment discontinuation related to safety or efficacy will be considered as non-responders.

The SAS code is available in Appendix 18.5.

The multiple imputations will be performed as follows:

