#### **Supportive analysis no. 4: Stratified difference of response rates with imputed ACR components using multiple imputations (MNAR pattern)**

The same method as in Supportive analysis no. 3 will be considered, but this time with MNAR pattern. Subjects' missing data due to early discontinuation will be imputed, using data available from the placebo arm, regardless of reason for study discontinuation.

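### Supportive analysis no. 4 can impute subjects who stopped for lack of efficacy or safety as ACR20 responders, so it changes the failure rule as well as the missing-data assumption

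*Protocol*

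**What the plan says.** **Protocol.** Section 5.5.1 deals with a subject who leaves treatment because RA is unacceptably high and needs therapy the protocol does not permit. That subject may "initiate therapy recommended per the treating physician. In this case, the subject will be considered a nonresponder". The adverse-event entry in the same list, "Adverse events, if permanent discontinuation of the IMP is desired or considered necessary by the Investigator and/or subject", gives no responder status. For the primary analysis, Section 8.5.2.1 covers stopping for any reason: "A subject will be considered as a nonresponder if the subject discontinues prior to Week 12". Sections 8.5.1 and 8.5.2.1 leave other imputation methods to the SAP, as sensitivity analyses of the primary endpoint.

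**SAP 14.1.** The primary analysis follows the protocol: "Subjects who prematurely discontinued from treatment will be considered as non-responders". Supportive analyses 1, 5 and 6 use the same LOCF-NR rule. The tipping-point analysis (no. 2) and the MAR multiple imputation (no. 3) share a narrower rule: "Subjects with reason of treatment discontinuation related to safety or efficacy will be considered as non-responders".

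No. 4 is introduced as the method of no. 3 with an MNAR pattern, but its text says that "missing data due to early discontinuation will be imputed, using data available from the placebo arm, regardless of reason for study discontinuation". Table 13 agrees: "using control-based approach, regardless of reasons for treatment discontinuation". The SAP gives no reason for dropping the non-responder rule, and SAP Section 7 does not mention it among the changes from the protocol.

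**The concern.** Under no. 4, a subject who stopped because the drug did not work, or because of an adverse event, is treated as having missing Week 12 components. Those components are imputed and may meet ACR20. For the subject described in 5.5.1, this contradicts the responder status that the protocol has already assigned. For safety stops, it departs from the rule used in the primary analysis and in nos. 2 and 3.

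Two things are at stake. First, moving from no. 3 to no. 4 changes both the missing-data assumption and who counts as a failure, so a gap between them cannot be put down to either. Second, readers usually take a control-based analysis to be the stricter one. Here it can give a larger treatment difference than the primary analysis when more subjects stop on drug than on placebo.

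**Working it through.** **Inputs from the plan.** Protocol 8.1 has 80 evaluable subjects per group, "assuming a placebo response proportion of 30% to 45% and an expected treatment benefit of 30%, after adjusting for multiple comparisons", a second effect size of 25 points with about 80% power, and about 11% dropout. Neither document splits dropout by arm or reason, so every split below is an assumption.

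**The plan's own figures.** 80/(1 - 0.11) = 89.9, which matches 90 enrolled per group. For 25 points, a two-sided chi-square test at 0.05/3 = 0.0167 gives 79.7% power at placebo rates of 30% and 45%, and 78.6% at the lowest point between. This matches the stated 80%. These figures only supply plausible rates; they do not decide the point.

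**Formulas.** In each arm let p be the completers' response, d the share stopping early, s the part of d related to safety or efficacy, o = d - s the rest, and q the mean imputed placebo-like response.
- Primary: (1 - d)p
- No. 3: (1 - d)p + o x p, taking the MAR mean as the arm's own completer rate
- No. 4 as written: (1 - d)p + d x q
- No. 4 restricted to other reasons: (1 - d)p + o x q

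With one q for both arms, no. 4 minus primary is q x (d on drug - d on placebo).

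**Illustration.** Assume completers at 60% on drug and 35% on placebo; d = 14% v 8%; s = 12% v 6%; o = 2% in each arm.
- Primary: 0.86 x 60 = 51.6 and 0.92 x 35 = 32.2; difference 19.4 points.
- No. 3: 51.6 + 0.02 x 60 = 52.8 and 32.2 + 0.02 x 35 = 32.9; difference 19.9.
- No. 4 as written: 19.4 + q x 6, which is 20.0 (q = 0.10), 20.6 (q = 0.20) or 21.5 (q = 0.35).
- No. 4 restricted: 19.4 + q x (2 - 2) = 19.4 for any q.

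The step from no. 3 to no. 4 splits into two parts. Changing only the missing-data assumption moves the difference by 19.4 - 19.9 = -0.5 points. Releasing the safety and efficacy stoppers then adds q x (12 - 6) = +0.6 to +2.1. The net is +0.1 to +1.6, so the second change hides the sign of the first.

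**Direction.** Assume a 25-point completer difference, with q equal to the placebo completer rate. The last column is the share of simulated trials below two-sided 0.0167 (binary stand-in for ACR20, 90 per arm, 1,500 trials, 100 imputations, Rubin's rules).

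| Completers, drug v placebo | Stops, drug v placebo | Primary | No. 4 as written | Simulated power |
|---|---|---|---|---|
| 55% v 30% | 11% v 11% | 22.25 | 22.25 | 78.1% to 74.5% |
| 55% v 30% | 15% v 7% | 18.85 | 21.25 | 59.3% to 68.3% |
| 55% v 30% | 20% v 5% | 15.5 | 20.0 | 44.2% to 62.3% |
| 70% v 45% | 20% v 5% | 13.25 | 20.0 | 27.9% to 58.4% |
| 55% v 30% | 7% v 15% | 25.65 | 23.25 | 89.7% to 76.1% |

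In the third row, if 5% in each arm stop for other reasons, the restricted version gives (44.0 + 0.05 x 30) - (28.5 + 0.05 x 30) = 45.5 - 30.0 = 15.5, the primary value.

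**Limit.** The planned model conditions on components at the previous visit, so q would depend on each subject's course before stopping. Some shift could then arise even with equal stopping.

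**The case against.** The other side has a good case on several points.

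- All-reasons control-based imputation is a recognised supportive analysis. It asks what response would be if stoppers then followed a placebo-like course. The all-reasons wording is in both text and table, so it looks deliberate, and the protocol expects sensitivity analyses to depart from the primary rule. This stands. It does not explain why a subject with a protocol-assigned nonresponder status is treated as missing, or why the analysis is presented as no. 3 with only the pattern changed.
- A reader might infer that Protocol 5.5.1 makes safety stops nonresponders too. It does not; its statement covers only unacceptably high RA needing non-permitted therapy. For safety stops the rule comes from Protocol 8.5.1 and 8.5.2.1 and from SAP 14.1.
- A reader might infer that no. 4 is built to favour evobrutinib. The documents do not support that: direction depends on which arm stops more, and stops for lack of efficacy could well be commoner on placebo.
- A reader might take no. 4 as the plan's only MNAR check. No. 2 is another. It varies the outcomes of missing subjects over all combinations, uses Hochberg, and keeps safety and efficacy stoppers as non-responders.
- No. 4 carries a nominal p-value only, and the SAP reports discontinuation reasons by arm, so an imbalance would be visible.
- The shift in the 14% v 8% illustration is small, and that pattern averages (8 + 3 x 14)/4 = 12.5% over four arms, slightly above the planned 11%.

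**Conclusion.** The point holds as a recommended correction to one supportive analysis. No. 4 conflicts with Protocol 5.5.1 for subjects who stop because of uncontrolled RA. It also departs from the non-responder rule for safety and efficacy stoppers in the primary analysis and in nos. 2 and 3. Its comparison with no. 3 therefore mixes two changes.

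Under the assumed 14% v 8% stopping, the difference rises from 19.4 to between 20.0 and 21.5 points. Larger imbalances move it by up to 6.75 points (20% v 5%, placebo 45%). With equal stopping it stays about level, and with more placebo stops it falls. The sizes rest on assumed stop rates by arm and on a single q. The finding that nos. 3 and 4 differ in two respects rests on the text alone.

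The primary conclusion is not affected. Nor do the documents show that no. 4 will overstate the effect in this trial; they show only that it cannot be relied on to be the stricter check.

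**What to change.** In SAP 14.1 no. 4 and the matching Table 13 entry, state that subjects whose treatment discontinuation is related to safety or efficacy remain non-responders, as in nos. 2 and 3. Apply control-based imputation only to components missing for other reasons. Nos. 3 and 4 then differ only in MAR versus control-based imputation.

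If the all-reasons version is kept, report it as a separately labelled row, say that it treats protocol-defined nonresponders as missing, and do not describe it as a conservative check.

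The cost is one SAP sentence, one table cell and one filter in the imputation program before unblinding, with no new data. The downside is that the restricted version imputes few subjects, so it will lie close to the primary result and may be slightly less favourable than no. 4 as written.
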